14.3 Analysis of Secondary Endpoints

Secondary endpoints include the following:

- The proportion of patients that can complete total neoadjuvant chemotherapy.
- The local control rate at 1 year will be described as percent with 95% confidence interval. Local control is defined as no local recurrence, calculated from RT start.
- The rate of grade 3 or higher toxicity will also be described as percent with 95% confidence interval.
- Kaplan-Meier estimates will be used to describe disease-free survival (no cancer evident or death) and overall survival (survival from start of RT) at 1 year.

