1.0 SCHEDULE OF ACTIVITIES

Bereening pro		t tane place	, ,, ,,,,,,,,,,,,,,,,,,,,,,,,,,,,,,,,,,	100 44	. ,,,,,	egibtita						
	Screening	Baseline	Fx1	Fx2	Fx3	Fx4	Fx5	Chemo ⁴	Surgery ⁵	3-mo F/U ⁶	6-mo F/U ⁶	12-mo F/U ⁶
Informed consent	Х											
H&P, ECOG PS	Х									Х		
CBC w/diff ¹	Х											
CMP ¹	Х											
Pregnancy test ²	Х											
EUS	Х											
Institutional MRI	Х											
screening questionnaire	Λ											
Simulation		Х										
CT C/A/P		Х							X^8		Х	Х
PET/CT		\mathbf{X}^{11}										
Adaptive SCRT ³			Х	Х	Х	Х	Х					
SOC chemotherapy ¹⁰								Х		Х		
Gastrectomy									X ⁹			
Research blood for		Х						X^7	X ⁷		X ⁷	
ctDNA		Λ						Λ	Λ		Λ	
AE assessment	AEs will be tracked from baseline through 12 months after surgery/definitive											
	end of treatment. Refer to Section 8.0 for more details.											

Screening procedures must take place within 60 days of registration.

1. labs will be drawn as per SOC

2. women of childbearing potential only

3. patients will receive 5 fractions of radiotherapy delivered once daily; radiotherapy may take up to 10 business days (due to logistical delays)

4. SOC chemotherapy will begin 2-4 weeks after completion of radiotherapy

5. within 2-4 weeks after completion of SOC chemo

6. follow-up visits will take place at 3 months (+/-2 weeks), 6 months (+/-4 weeks), and 12 months (+/-4 weeks) post-surgery; patients who don't undergo surgery will have follow-up visits at 3 months (+/-2 weeks), 6 months (+/-4 weeks), and 12 months (+/-4 weeks) from the date of definitive end of treatment.

7. after completion of RT / prior to starting chemo, at completion of chemo / prior to surgery, and 6 months after surgery. See Section 9.2 for further details.

8. prior to surgery

9. tissue for research will be collected from patients who experience pCR

10. Any SOC total neoadjuvant chemotherapy regimen may be given at the discretion of and under the supervision of the treating medical oncologist

11. PET/CT is strongly encouraged at baseline but optional

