6.3 Chemotherapy Guidelines

Chemotherapy will be given as per standard of care and should begin 2 to 4 weeks after completion of radiotherapy. Recommended total neoadjuvant chemotherapy regimens are:

- CAPOX (capecitabine/oxaliplatin)
- FOLFOX (oxaliplatin, leucovorin, and 5-FU)
- FLOT (docetaxel, oxaliplatin, leucovorin, and 5-FU)

However, the treating medical oncologist may prescribe other SOC total neoadjuvant chemotherapy regimen upon discussion with the WUSM PI. Additionally, if one regimen is not tolerated, subjects can move between regimens for a goal of 4 months of chemotherapy treatment total prior to surgery.

Patients who are unable to complete their total neoadjuvant therapy regimen may complete the chemotherapy postoperatively, at the discretion of the treating physician. Postoperative chemotherapy should start within 3 months of surgery. Patients who are medically inoperable will continue to receive chemotherapy until the entire regimen is complete.

A maximum (cumulative) delay of treatment of 4 weeks (or single delay of 3 weeks) is allowed per protocol due to factors/AEs listed in Section 7.0 (i.e., chemotherapy should be completed within a 5-month period). Cumulative delays in excess of 4 weeks, or single delays in excess of 3 weeks, will need to be discussed with the Principal Investigator in regard to proceeding to surgical resection. Such cases will need to be individualized depending on the clinical scenario. Please note that chemotherapy administration and AE assessment should be performed under the supervision of a medical oncologist. Dosing is to follow standard of care recommendations per institutional guidelines.

Interval imaging during chemotherapy, if obtained, is at the discretion of the treating physician.

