6.6 Definitions of Evaluability

Local control rate at 1 year post RT	Have received at least one fraction of
	radiation therapy and undergone at
	least one disease assessment
Rate of grade 3 or greater toxicity	Have received at least one fraction of
Rate of grade 5 of greater toxicity	
	radiation therapy
Overall survival at 1 year post RT	Have received at least one fraction of
	radiation therapy
Disease-free survival at 1 year post RT	Have received at least one fraction of
	radiation therapy and undergone at
	least one disease assessment
Exploratory	
Average percent difference in coverage of	Have received at least one fraction of
PTV by 95% isodose line	radiation therapy
Average percentage difference in dose to	Have received at least one fraction of
nearby OARs due to variation in OAR	radiation therapy
position	
Percentage of patients in each TCGA	Have completed radiation therapy and
molecular subtype after radiation and	neoadjuvant chemotherapy
chemotherapy	
Specific biomarkers	Have had specimens collected for
·	biomarkers
ctDNA	Have had specimens collected for
	biomarkers

Note that inevaluable patients will not be replaced.

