6.10 Duration of Follow-up

Patients will be followed for local recurrence, distant recurrence, and toxicity for 12 months after surgery (or date of definitive end of treatment for patients who do not have surgery). Follow-up visits will be include the following:

- 3-month follow-up: H&P, ECOG PS.
- 6-month follow-up: CT C/A/P, blood for ctDNA.
- 12-month follow-up: CT C/A/P

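### One-year local control is planned as a percent with no rule for patients lost before month 12; read literally, a patient lost after the pre-surgery CT would count as controlled

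*Combined protocol and SAP*

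**What the plan says.** - **Measure.** Section 14.3: "The local control rate at 1 year will be described as percent with 95% confidence interval". The interval method is not named.
- **Event and origin.** Section 14.3: "Local control is defined as no local recurrence, calculated from RT start".
- **Contrast.** The same section assigns a censoring method to two other endpoints: "Kaplan-Meier estimates will be used to describe disease-free survival (no cancer evident or death") and overall survival. Local control is not among them.
- **Denominator.** Section 6.6 requires one RT fraction and at "least one disease assessment". It sets no minimum follow-up and does not require surgery. Inevaluable patients are not replaced.
- **Scans.** In Section 1.0 the only CT between baseline and the 6-month follow-up carries the footnote "8. prior to surgery". The later CTs are at "6 months (+/-4 weeks), and 12 months (+/-4 weeks) post-surgery".
- **Status form.** Section 10.0 schedules a Local Control Form 12 months after RT start.
- **Loss to follow-up.** Section 6.11 covers contact attempts and classes the patient as withdrawn. It gives no analysis rule.
- **Unresected patients.** Section 6.3: "Patients who are medically inoperable will continue to receive chemotherapy until the entire regimen is complete". Section 6.10 gives the scope of follow-up as "local recurrence, distant recurrence, and toxicity for 12 months after surgery (or date of definitive end of treatment for patients who do not have surgery"). Section 6.5 records local failure without defining it, and Section 11.0 says that radiographic response is neither recorded nor assessed.

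**The concern.** A percent at a fixed time needs a known status for every patient in the denominator. Section 6.6 admits patients whose status at 1 year may be unknown, and Section 14.3 does not say what to do with them. The literal event definition is met by the absence of a recorded recurrence, so a patient observed for about half the year would pass as controlled for all of it. That scoring errs only towards better local control. Section 2.3.2 plans to compare clinical outcomes with historical controls, although Section 14 gives no local-control benchmark.

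A related gap is the event itself. Patients without surgery are excluded from pCR evaluability but not from local control. A primary that was never removed and then grows is arguably not a recurrence, and no section says how it is scored. Left open, that choice would be made after the data are seen.

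**Working it through.** **The plan's own figure.** The only planning figure is for pCR: 20% with 36 patients, interval 9% to 37%. A Clopper-Pearson interval with x = 0.20 × 36 = 7.2 and n = 36 gives 8.6% to 36.7%, which rounds to the stated values. No figure is given for local control.

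**Timing from the protocol's windows** (month = 30.44 days; RT 1–2 weeks, gap 2–4 weeks, chemotherapy 4–5 months, gap 2–4 weeks).
- Earliest surgery: (1 + 2 + 2) weeks + 4 months = 5.1 months after RT start.
- Latest surgery: (2 + 4 + 4) weeks + 5 months = 7.3 months.
- The pre-surgery CT falls at or shortly before surgery, so about 5 to 7 of the 12 months are observed.
- 6-month CT (± 4 weeks): 10.2 to 14.2 months. With mid-window gaps, 1 week of RT and 4 months of chemotherapy: 11.6 months.

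**Losses on the CT schedule.** The documents give no loss or failure rate. Assume 36 evaluable, L lost after the pre-surgery CT, and f failures all found on the 6-month CT. Lost patients scored as controlled: 1 − f/36. Censored: 1 − f/(36 − L).

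| f | L | As controlled | Censored | Difference |
|---|---|---|---|---|
| 4 | 2 | 88.9% | 88.2% | 0.7 |
| 4 | 4 | 88.9% | 87.5% | 1.4 |
| 6 | 2 | 83.3% | 82.4% | 1.0 |
| 6 | 4 | 83.3% | 81.2% | 2.1 |
| 9 | 2 | 75.0% | 73.5% | 1.5 |
| 9 | 4 | 75.0% | 71.9% | 3.1 |

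If the L patients are dropped instead, the percent is (36 − L − f)/(36 − L), which equals the censored column.

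**Losses spread over the year.** Assume exponential times with monthly hazards a (local failure), b (death) and c (loss), each −ln(1 − p)/12. True incidence is a/(a+b) × [1 − exp(−12(a+b))]. The crude failure share is a/(a+b+c) × [1 − exp(−12(a+b+c))]. With failure 25%, death 10% and loss 10%: 0.7319 × 0.3250 = 23.8% against 0.5772 × 0.3925 = 22.7%, a difference of 1.1 points. Over failure 10–25% and death 10–30%, the difference is 0.2–0.6 points at 5% loss, 0.4–1.1 at 10%, and zero with no loss. Deaths alone therefore create no error.

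**Unresected primaries.** Each patient scored one way rather than the other moves the result by 1/36 = 2.8 points. With four other failures, two such patients give 88.9% or 83.3%; four give 88.9% or 77.8%. These counts are assumed.

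**Scans after month 12.** With uniform draws within the windows (1,000,000), 35% of 6-month CTs fall after month 12 if chemotherapy takes 4 months, and 62% if it takes 4 to 5 months. If all failures were first seen on that CT, the share missed at 1 year at 35% is 0.35 × 4/36 = 3.9 points to 0.35 × 9/36 = 8.8 points. At 62% it is 6.9 to 15.5 points.

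**Scale.** The exact 95% interval for 32/36 is 73.9% to 96.9%, about 23 points wide.

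**The case against.** The strongest case is that the plan never says that a lost patient is scored as controlled. A reader might infer a stated wrong rule, or a percent that can only err upward. The documents support neither: Section 14.3 has no rule for unknown status, and the Local Control Form due at 12 months would hold no informative status for such a patient, so missing is as natural a data state as controlled. If missing patients were left out, the error in the table would be zero. This stands, and the upward error is conditional on the scoring. But leaving them out contradicts Section 6.6, which counts them as evaluable, so a rule is needed either way.

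The even-loss figures may also be too high. Unless the baseline CT counts as a disease assessment, a term that Section 6.6 leaves undefined, patients lost before the first assessment after RT leave the denominator.

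The late-scan effect can exceed the loss correction. That is fair and has to be reported beside the fix, but a strict scan-date reading of the current plan has the same limitation.

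A reader might also infer that the plan leaves unresected progression out of local failure. It does not say so: Section 6.10 follows these patients for local recurrence, so the intent is probably to count them. This is a gap in definition. Section 11.0 adds that the basis for calling progression is not given.

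**Conclusion.** The point holds as a minor one. The literal text would count a patient lost after the pre-surgery CT as controlled, and nothing in the documents excludes or censors that patient. If scored so, the percent is too high by about 0.7 to 3.1 points with 2 to 4 of 36 lost and 4 to 9 failures, and by about 0.2 to 1.1 points with 5–10% loss spread over the year. All loss and failure rates are assumptions. Both effects are small against an interval about 23 points wide.

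The scoring of unresected primaries could matter more per patient, but its size depends on a count that the documents do not give. The time origin is a wording matter: Sections 3.0 and 6.6 count from RT without saying start or end, Section 14.3 uses RT start for local control and overall survival, and gives none for disease-free survival. RT takes 1 to 2 weeks, so the difference is no larger.

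Nothing here touches pCR, the sample size or any formal test.

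**What to change.** In Section 14.3:
1. Estimate 1-year local control from RT start as 1 minus the cumulative incidence of local failure (Aalen-Johansen), with death without local failure as a competing event and censoring at the last disease assessment. This matches the censoring already used for disease-free and overall survival.
2. State that local failure includes local progression of an unresected primary, taken from the local failure item (Section 6.5) and the Progression Form (Section 10.0). Because Section 11.0 rules out radiographic response assessment, state the basis on which progression is called.
3. Use RT start as the origin throughout, and align Sections 3.0 and 6.6. The Local Control Form is already timed from RT start.
4. Report actual scan times, do not backdate findings, and say that failures first seen on a CT after month 12 are not counted at 1 year. This could raise the estimate by about 4 to 9 points in the 4-month chemotherapy case above, and by more if chemotherapy runs longer.

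The cost is a few sentences and a standard competing-risks routine, with no change to visits, scans or patient numbers. The forms already exist; only the stated basis for progression is new. The estimate may be slightly less favourable.

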14.4 Baseline Descriptive Statistics

Baseline demographic characteristics will be summarized: Continuous factors will be presented as median with range; categorical factors will be presented as counts and percentages.

15.0 MULTICENTER REGULATORY REQUIREMENTS

Washington University requires that each participating site sends its informed consent document to be reviewed and approved by the WUSM Regulatory Coordinator (or designee) prior to IRB/IEC submission.

Site activation is defined as when the secondary site has received official written documentation from the coordinating center that the site has been approved to begin enrollment. At a minimum, each participating institution must have the following documents on file at Washington University prior to study activation:

- Documentation of IRB approval of the study in the form of a letter or other official document from the participating institution's IRB. This documentation must show which version of the protocol was approved by the IRB.
- Documentation of IRB approval of an informed consent form. The consent must include a statement that data will be shared with Washington University, including the Quality Assurance and Safety Monitoring Committee (QASMC), the DSMC (if applicable), and the Washington University study team.
- Documentation of FWA, signed FDA Form 1572 (if applicable), and the CVs of all participating investigators.
- Protocol signature page signed and dated by the investigator at each participating site.

The coordinating center Principal Investigator (or designee) is responsible for disseminating to the participating sites all study updates, amendments, reportable adverse events, etc. Protocol/consent modifications and IB updates will be forwarded electronically to the secondary sites within 4 weeks of obtaining Washington University IRB approval. Activated secondary sites are expected to submit protocol/consent/IB modifications to their local IRBs within 4 weeks of receipt unless otherwise noted. Upon the secondary sites obtaining local IRB approval, documentation of such shall be sent to the Washington University study team within 2 weeks of receipt of approval.

Documentation of participating sites' IRB approval of annual continuing reviews, protocol amendments or revisions, all SAE reports, and all protocol violations/deviations/exceptions must be kept on file at Washington University.

The investigator or a designee from each institution must participate in a regular conference call to update and inform regarding the progress of the trial.

APPENDIX A: ECOG Performance Status Scale

Grade	Description
0	Normal activity. Fully active, able to carry on all pre-disease performance without restriction.
1	Symptoms, but ambulatory. Restricted in physically strenuous activity, but ambulatory and able to carry out work of a light or sedentary nature (e.g., light housework, office work).
2	In bed <50% of the time. Ambulatory and capable of all self-care, but unable to carry out any work activities. Up and about more than 50% of waking hours.
3	In bed >50% of the time. Capable of only limited self-care, confined to bed or chair more than 50% of waking hours.
4	100% bedridden. Completely disabled. Cannot carry on any self-care. Totally confined to bed or chair.
5	Dead.

APPENDIX B: Definitions for Adverse Event Reporting

A. Adverse Events (AEs)

As defined in 21 CFR 312.32:

Definition: any untoward medical occurrence associated with the use of a drug in humans, whether or not considered drug-related.

Grading: the descriptions and grading scales found in the revised NCI Common Terminology Criteria for Adverse Events (CTCAE) version 5.0 will be utilized for all toxicity reporting. A copy of the CTCAE version 5.0 can be downloaded from the CTEP website.

Attribution (relatedness), Expectedness, and Seriousness: the definitions for the terms listed that should be used are those provided by the Department of Health and Human Services' Office for Human Research Protections (OHRP). A copy of this guidance can be found on OHRP's website:

http://www.hhs.gov/ohrp/policy/advevntguid.html

B. Suspected Adverse Reaction (SAR)

As defined in 21 CFR 312.32:

Definition: any adverse event for which there is a reasonable possibility that the drug caused the adverse event. "Reasonable possibility" means there is evidence to suggest a causal relationship between the drug and the adverse event. "Suspected adverse reaction" implies a lesser degree of certainty about causality than adverse reaction, which means any adverse event caused by a drug.

C. Life-Threatening Adverse Event / Life Threatening Suspected Adverse Reaction

As defined in 21 CFR 312.32:

Definition: any adverse drug event or suspected adverse reaction is considered "lifethreatening" if, in the view of the investigator, its occurrence places the patient at immediate risk of death. It does not include an adverse event or suspected adverse reaction that, had it occurred in a more severe form, might have caused death.

D. Serious Adverse Event (SAE) or Serious Suspected Adverse Reaction

As defined in 21 CFR 312.32:

Definition: an adverse event or suspected adverse reaction is considered "serious" if, in the view of the investigator, it results in any of the following outcomes:

- o Death
- A life-threatening adverse event

- Inpatient hospitalization or prolongation of existing hospitalization
- A persistent or significant incapacity or substantial disruption of the ability to conduct normal life functions
- A congenital anomaly/birth defect
- Any other important medical event that does not fit the criteria above but, based upon appropriate medical judgment, may jeopardize the subject and may require medical or surgical intervention to prevent one of the outcomes listed above

E. Protocol Exceptions

Definition: A planned change in the conduct of the research for one participant.

F. Deviation

Definition: Any alteration or modification to the IRB-approved research without prospective IRB approval. The term "research" encompasses all IRB-approved materials and documents including the detailed protocol, IRB application, consent form, recruitment materials, questionnaires/data collection forms, and any other information relating to the research study.

A minor or administrative deviation is one that does not have the potential to negatively impact the rights, safety, or welfare of participants or others or the scientific validity of the study.

A major deviation is one that does have the potential to negatively impact the rights, safety, or welfare of participants or others or the scientific validity of the study.

APPENDIX C: Reporting Timelines

Expedited Reporting Timelines				
Event	HRPO	QASMC		
Unanticipated problem	Report within 10 working days. If the	Report via email after IRB		
involving risk to participants or	event results in the death of a participant	acknowledgment		
others	enrolled at WU/BJH/SLCH, report			
	within 1 working day.			
Major deviation	Report within 10 working days. If the			
	event results in the death of a participant			
	enrolled at WU/BJH/SLCH, report			
A series of minor deviations	within 1 working day.			
that are being reported as a	Report within 10 working days.			
continuing noncompliance				
Protocol exception	Approval must be obtained prior to			
1 lotocol exception	implementing the change			
Complaints	If the complaint reveals an unanticipated			
	problem involving risks to participants			
	or others OR noncompliance, report			
	within 10 working days. If the event			
	results in the death of a participant			
	enrolled at WU/BJH/SLCH, report			
	within 1 working day. Otherwise, report			
	at the time of continuing review.			
Breach of confidentiality	Within 10 working days.			
Incarceration	If withdrawing the participant poses a			
	safety issue, report within 10 working			
	days.			
	If with drawing the norticing at damaged			
	If withdrawing the participant does not			
	represent a safety issue and the patient will be withdrawn, report at continuing			
	review.			
	10110111			

	Routine Reporting Timelines					
Event	HRPO	QASMC				
Adverse event or SAE that does not require expedited reporting	If they do not meet the definition of an unanticipated problem involving risks to participants or others, report summary information at the time of continuing review	Adverse events will be reported in the toxicity table in the DSM report which is typically due every 6 months.				
Minor deviation	Report summary information at the time of continuing review.					
Complaints	If the complaint reveals an unanticipated problem involving risks to participants or others OR noncompliance, report within 10 working days. If the event results in the death of a participant enrolled at WU/BJH/SLCH, report within 1					

Routine Reporting Timelines					
Event	Event HRPO				
	working day. Otherwise, report at the time of				
	continuing review.				
Incarceration	Incarceration If withdrawing the participant poses a safety issue, report within 10 working days.				

Expedited Reporting Timelines for Secondary Sites				
Event	Local IRB			
Serious AND unexpected	Report no later than 11 calendar days	Report all applicable events		
suspected adverse reaction	after it is determined that the information	to local IRB according to		
	qualifies for reporting.	local institutional guidelines.		
Unexpected fatal or life-	Report no later than 4 calendar days after			
threatening suspected	initial receipt of the information.			
adverse reaction				
Unanticipated problem	Report no later than 4 calendar days after			
involving risk to participants	initial receipt of the information.			
or others				
Adverse event or SAE that	As per routine data entry expectations			
does not require expedited				
reporting				
Protocol exception	Approval must be obtained prior to			
	implementing the change.			

